Diabetes control is often assessed by tests of glucose levels over time, such as the glycosylated hemoglobin A1c (HbA1c) and fructosamine. In the later stages of chronic kidney disease (CKD) there is limited data available on the utility of these tests. There are reasons to believe that the tests may be less accurate in this population. Continuous glucose monitoring (CGM) offers an effective method for understanding the totality of glucose exposure and incidence of both hyperglycemic and hypoglycemic excursions. In the proposed study we plan to utilize CGM in patients with late stage CKD stages 3b-5 to 1) determine accuracy of HbA1c and serum fructosamine testing as measures of glucose control in patients with Type 2 Diabetes Mellitus (T2DM), 2) better understand test characteristics in the late stage CKD population (correlation, linear equation, slope, Y intercept, average glucose at different HbA1c levels), 3) develop a preliminary understanding of how test characteristics differ in late stage CKD compared to other patients with diabetes, 4) quantify time burden and number of episodes of hypoglycemia, 4) study hyperglycemic burden and 5) analyze glucose variability. The research staff will explain the study to patients that meet all inclusion criteria. Patients will get time to understand the study, review the consent document, ask questions to the PI, and then provide their consent to participate in the study. On Day 1 of the study, a CGM (Freestyle Libre) device will be placed on patients with CKD 3b-5 which will be worn for 14 consecutive days. Patients will return on Day 14 to remove the CGM device. HbA1c and fructosamine values will be drawn on Day 14 and these results will be compared with average glucose monitoring values as recorded on the CGM device. Incidence, duration, and severity of both hypoglycemic and hyperglycemic events will be analyzed. It is our hypothesis that there will be significant variability in the serum HbA1c values when compared with calculated HbA1c from CGM readings. We also hypothesize that the results will reflect a greater incidence of hypoglycemia in this population by CGM analysis.

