4. OBJECTIVE(S)/SPECIFIC AIMS AND HYPOTHESES

- *A concise statement of the goal(s) of the current study.*
- *The rationale for and specific objectives of the study.*
- *The goals and the hypothesis to be tested should be stated.*

- The goals of our study is to 1) determine accuracy of HbA1c and serum fructosamine testing as measures of glucose control, 2) better understand test characteristics in the late stage CKD population (correlation, linear equation, slope, Y intercept, average glucose at different HbA1c levels), 3) develop a preliminary understanding of how

test characteristics differ in late stage CKD compared to other patients with diabetes, 4) quantify time burden and number of episodes of hypoglycemia, 5) study hyperglycemic burden and 6) analyze glucose variability.

- It is our hypothesis that there will be significant variability in the serum HbA1c values when compared with calculated HbA1c from CGM readings. It is our hypothesis than the incidence of hypoglycemia will be high in patients with CKD 3b-5.

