8. NUMBER OF SUBJECTS

- *Indicate the total number of subjects to be accrued locally. If applicable, distinguish between the number of subjects who are expected to be pre-screened, enrolled (consent obtained), randomized and complete the research procedures.*
- *If your study includes different cohorts, include the total number of subjects in each cohort.*
- *If this is multisite study, include total number of subjects across all sites.*

There is an expected number of 80 recruited subjects from all aforementioned sites (Northwell Health Division of Nephrology, Division of Endocrinology, and Winthrop University Hospital Division of Nephrology).
We expect all patients will complete the research procedures

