10. ENDPOINTS

- *Describe the primary and secondary study endpoints*
- *Describe any primary or secondary safety endpoints*

- Primary End-Points: 1) Correlation between HbA1c and mean glucose concentration measured by CGM; 2) Characterization of hypoglycemic events, number, severity and duration. (Also, a safety end-point).
- Secondary End-Points: 1) Correlation between serum fructosamine and mean glucose concentration measured by CGM, 2) Determination of HbA1c and serum fructosamine regression equation, slope, Y intercept, average glucose at different test levels, 3) Number of hyperglycemic events and duration of each hyperglycemic event, 4) Study glucose variability as measured by mean amplitude of glucose excursion

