- The FreeStyle Libre Pro Flash Glucose Monitoring System is a professional continuous glucose monitoring (CGM) device indicated for detecting trends and tracking patterns in persons (age 18 and older) with diabetes. The Freestyle Libre Pro device is FDA approved (PMA# P150021). Participants will use the FreeStyle Libre Pro Flash Glucose Monitoring device according to its approved use, on the back of the arm.
- CGM monitoring will be performed on Day 1 by placing the Freestyle Libre Pro on research subjects for intended use of 14 days.
- Subjects will be advised to return to the research site on Day 14 to remove the CGM device for analysis. On Day 14, blood will be drawn for HbA1c and fructosamine, funded by internal research funds and there will be no charge to the patient. The blood drawn for this research will be approximately 10-15 milliliters.
- There are no drug washout periods. Subjects will continue to take all their medications and/or insulins as prescribed by their doctor.
- Baseline data including age, race, ethnicity, past medical history, home medication list, and diabetes related laboratory data will be collected from Allscripts medical records. No personal identifying information will be collected.

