12. STATISTICAL ANALYSIS

- *Describe how your data will be used to test the hypotheses.*
- *State clearly what variables will be tested and what statistical tests will be used.*
- *Include sample size calculations.*
- *If this is a pilot study, state which variables will be examined for hypothesis generation in later studies.*

Patients with less than 7 days of CGM measurements will be excluded from analysis. Arithmetic mean glucose (AMG) will be calculated for each patient from

all CGM glucose measurements. A simple linear regression model will be applied to estimate the relationship between AMG and HbA1c. Once the relationship is established through the model, prediction of mean AMG together with 95% confidence intervals will be calculated at different levels of HbA1c. Influence of factors such as age, gender on the relationship between HbA1c and AMG will be examined through a multivariate regression model. Slopes and intercepts of the regression equations for the individual subgroups will be compared to those of the simple linear regression model. A quadratic regression model will also be applied if the relationship between the two variables is not linear. The same analysis will be performed to establish the relationship between AMG and serum fructosamine. Linear and quadratic regression models will be applied to estimate the relationship between AMG and HbA1c and serum fructosamine. If a linear relationship is established then slope, Y-intercept and correlation coefficient will be calculated. Mean AMG at different levels of HbA1c and serum fructosamine will be calculated. Glucose variability will be calculated as MAGE scores. First all the local maximum/minimum values are determined. The next step is an assessment of maximum/minimum pairs against the standard deviation (SD). If the difference from minimum to maximum is greater than the SD, this variation from mean measure is retained. If the local maximum/minimum is less than 1 SD it is excluded from further calculations. These troughs are retained and summed to achieve the MAGE score.

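### The hyperglycemia endpoint (event number and duration of each event) is never combined into time above a cut-off or adjusted for days worn, so it is a poor measure of the burden named in the aims

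*Combined protocol and SAP*

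**What the plan says.** Section 4 ends its list of goals with "4) quantify time burden and number of episodes of hypoglycemia, 5) study hyperglycemic burden and 6) analyze glucose variability". Time is named for hypoglycemia only. The hyperglycemia goal is worded as burden.

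In section 10, secondary end-point 3 serves that goal: "3) Number of hyperglycemic events and duration of each hyperglycemic event". Hypoglycemia sits in primary end-point 2: "Characterization of hypoglycemic events, number, severity and duration". The lay summary in section 2 adds "Incidence, duration, and severity of both hypoglycemic and hyperglycemic events will be analyzed", again without naming a summary measure.

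Section 12 defines two CGM summaries, the arithmetic mean glucose (AMG) and MAGE. It gives no analysis of hyperglycemic or hypoglycemic events: no cut-off, no rule for when an event starts or ends, no total or percentage of time beyond a cut-off, and no rate per day. On wear time, section 11 places the sensor "for intended use of 14 days", and section 12 states: "Patients with less than 7 days of CGM measurements will be excluded from analysis". Analyzed patients may therefore contribute anything from 7 to 14 days.

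**The concern.** Burden means how much of the time glucose is high. A count of excursions does not rise steadily with that. Each event needs an upward crossing of the cut-off. Crossings are most frequent when a patient's mean lies near the cut-off and become rarer as the mean moves well above it, because separate excursions join into long ones. Over that upper range, a higher count means a lower burden.

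Listing how long each event lasts supplies the missing information only if the durations are added up within each patient. The plan does not say that they will be. A mean or median per event is not burden either.

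Raw counts also grow with the number of days recorded, which is not the same for every analyzed patient. That applies equally to the hypoglycemia count in a primary end-point. At stake is whether the reported figures answer goal 5, and whether part of goal 4 reflects how long the sensor stayed on.

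**Working it through.** The documents give no figure for this endpoint, so there is nothing to reproduce.

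**Inputs from the documents.** Planned wear is 14 days = 14 × 24 = 336 h (section 11). Minimum wear for analysis is 7 days (section 12).

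**Assumptions, not in the documents.** An event is an unbroken run above a cut-off. Cut-offs of 180 and 250 mg/dL, within-patient variability, and the 15-minute spacing of simulated readings are chosen for illustration only.

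**Step 1: the limiting case.** A trace always above the cut-off is 1 event of 336 h. A trace never above it is 0 events.

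**Step 2: closed form.** Take a smooth stationary Gaussian trace (Gaussian kernel, SD s = 2 h). Let z = (cut-off − mean)/SD. By Rice's formula, the up-crossing rate at the mean is √(1/(2s²))/(2π) = 0.3536/6.283 = 0.0563 per hour, or 18.9 per 336 h. Then

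expected events = 18.9 × exp(−z²/2) + P(trace starts above the cut-off).

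With cut-off 180 and a fixed SD of 50:

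| Mean (mg/dL) | z | Expected events | Time above |
|---|---|---|---|
| 120 | 1.2 | 18.9 × 0.487 + 0.12 = 9.3 | 12% |
| 180 | 0 | 18.9 + 0.5 = 19.4 | 50% |
| 240 | −1.2 | 18.9 × 0.487 + 0.88 = 10.1 | 88% |
| 300 | −2.4 | 18.9 × 0.056 + 0.99 ≈ 2 | 99% |

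The near-equal counts at 120 and 240 follow from holding the SD fixed. With SD proportional to the mean (CV 25% to 33%), the same formula gives about 3 to 6 events at mean 120, 19 at 180, 12 to 15 at 240 and 6 to 10 at 300. The fall above 180 remains; the equality does not.

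**Step 3: a different trace model.** Simulated 15-minute readings over 14 days: autocorrelated noise with a 2 h time constant plus a three-cycle daily pattern, 40 traces per setting. Cut-off 180, CV 25%:

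| Mean (mg/dL) | Events | Total h above | Mean h per event | Time above |
|---|---|---|---|---|
| 120 | 10.2 | 6.4 | 0.64 | 2% |
| 140 | 47.7 | 42.7 | 0.90 | 13% |
| 180 | 83.4 | 168.3 | 2.03 | 50% |
| 240 | 56.8 | 279.2 | 4.98 | 83% |
| 300 | 26.4 | 317.8 | 12.66 | 95% |
| 340 | 14.3 | 327.9 | 28.52 | 98% |

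Total hours rise throughout; the count does not. Other settings keep the shape. At cut-off 180 and CV 33%, the peak is 83 events at mean 180, falling to 35 at 340. At cut-off 250 and CV 25%, the peak is 85 at mean 260, falling to 52 at 340. Absolute counts depend heavily on the model (19 against 83 at mean 180), so only the shape should be relied on.

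**Step 4: a cohort of the planned size.** In one simulated cohort of 80 (patient means about 175, SD 45, CV 28%, cut-off 180), the rank correlation of mean glucose with event count was 0.57 overall and −0.85 among the 21 with a mean above 200. With total hours above the cut-off it was 0.996 overall.

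**Step 5: duration per event.** In the step 3 table, mean duration rises with burden but not in proportion. From mean 180 to 340, total time goes up by 327.9/168.3 = 1.9 times and mean duration by 28.52/2.03 = 14 times. Nor does it identify burden: ten 2-hour events (20 h) and one 2-hour event (2 h) share a mean and median of 2 h.

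**Step 6: wear time.** At mean 180 and SD 50, the second model gave 43.1 events in 7 days and 85.4 in 14. Per day these are 43.1/7 = 6.2 and 85.4/14 = 6.1, and time above was 50% in both. The raw count halves; the rate and the percentage do not move.

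**The case against.** The strongest reply is that the endpoint is not a count alone. Summed within a patient, the listed durations are total time above the cut-off, which is exactly the burden measure wanted. This stands: the data are sufficient, and the fault is an unstated summary. A reader might infer that the study cannot answer goal 5; the documents do not support that.

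A reader might also infer that the most hyperglycemic patients score best, or that the plan will put patients or CKD subgroups in the wrong order. Neither follows. A patient never above the cut-off has 0 events and one always above has 1, and across the whole simulated cohort count and mean glucose were positively related. Nothing in the plan ranks patients by event count, compares subgroups on hyperglycemia, pools events across patients or takes a median event duration. Subgroups appear in section 12 only for the regression of AMG on the laboratory markers.

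On wear time, everyone is meant to wear the sensor for 14 days and section 8 expects all subjects to complete. Seven days is the floor, so a twofold difference is the extreme, and no distribution of wear is given.

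On hypoglycemia, duration is already part of primary end-point 2, and the merging argument has not been shown for low glucose. Only the missing denominator and the unstated time summary carry over.

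Finally, the plan does not define an event. The rise and fall is derived for unbroken runs above a cut-off, and another event rule could change it.

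**Conclusion.** The concern holds in a limited form. As written, the hyperglycemia endpoint is a poor measure of burden because its count rises until about half the time is above the cut-off and then falls, and because the plan does not say that durations will be summed per patient or set against recorded time. The direction rests on one assumption, that an event is an unbroken run above a cut-off. The size rests on assumed cut-offs and variability and should not be quoted as a prediction for this study. Unequal wear adds at most a factor of two to raw counts of either kind at the same event rate.

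The consequence is confined to how hyperglycemic burden and hypoglycemia frequency are reported. The hyperglycemia endpoint is secondary and descriptive, AMG still reflects overall exposure, and the primary correlation of HbA1c with CGM mean glucose is untouched. This is a worthwhile, inexpensive improvement, not a flaw that undermines the study.

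**What to change.** In sections 10 and 12:

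- Make each patient's percentage of recorded CGM time above a pre-specified cut-off the measure of hyperglycemic burden.
- For hypoglycemia in primary end-point 2, add each patient's percentage of recorded time below a pre-specified cut-off, and events per day of wear.
- Keep hyperglycemic event number (per day of wear) and event duration as descriptive items, with the cut-offs and the rules for the start and end of an event written down before analysis. The choice of cut-offs is for the investigators.
- Summarize across patients, with one value per patient, rather than across pooled events.

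The cost is wording only. The same CGM download supplies every quantity, with no extra visits, tests or subjects. The small downside is that event counts become descriptive.

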11. RESEARCH PROCEDURES

- *Include a detailed description of all procedures to be performed on the research subject and the schedule for each procedure.*
- *Include any screening procedures for eligibility and/or baseline diagnostic tests*
- *Include procedures being performed to monitor subjects for safety or minimize risks*
- *Include information about drug washout periods*
- *If drugs or biologics are being administered provide information on dosing and route of administration*
- *Clearly indicate which procedures are only being conducted for research purposes.*
- *If any specimens will be used for this research, explain whether they are being collected specifically for research purposes.*
- *Describe any source records that will be used to collect data about subjects*
- *Indicate the data to be collected, including long term follow-up*

- During the initial pre-screening visit, Day 0, the study will be explained to subjects and informed consent will be obtained after all subject questions have been answered by the investigators and the patient had adequate time to review all documentation and understand their role as a

voluntary participant. A chart review will be performed to evaluate baseline, complete blood count profile (CBC), and basic metabolic profile (BMP) completed within the previous 12 weeks that will determine if the subject meets inclusion criteria for the study. If subjects meet inclusion criteria then they will return to the research site on Day 1 to place Freestyle Libre Pro device by the research staff for 14-day monitoring. If baseline laboratory tests were performed prior to 12 weeks from Day 0, then a blood sample will be collected on Day 0 for baseline CBC and BMP laboratory tests that will be billed to the patient's insurance. If subjects meet inclusion criteria based on blood results collected on Day 0, they will be advised to come to the clinic on Day 1 to place a Freestyle Libre Pro device by the research staff. If subjects do not meet inclusion criteria based on blood results collected on Day 0, then they will be excluded from the study.

- The FreeStyle Libre Pro Flash Glucose Monitoring System is a professional continuous glucose monitoring (CGM) device indicated for detecting trends and tracking patterns in persons (age 18 and older) with diabetes. The Freestyle Libre Pro device is FDA approved (PMA# P150021). Participants will use the FreeStyle Libre Pro Flash Glucose Monitoring device according to its approved use, on the back of the arm.
- CGM monitoring will be performed on Day 1 by placing the Freestyle Libre Pro on research subjects for intended use of 14 days.
- Subjects will be advised to return to the research site on Day 14 to remove the CGM device for analysis. On Day 14, blood will be drawn for HbA1c and fructosamine, funded by internal research funds and there will be no charge to the patient. The blood drawn for this research will be approximately 10-15 milliliters.
- There are no drug washout periods. Subjects will continue to take all their medications and/or insulins as prescribed by their doctor.
- Baseline data including age, race, ethnicity, past medical history, home medication list, and diabetes related laboratory data will be collected from Allscripts medical records. No personal identifying information will be collected.

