3. INTRODUCTION/BACKGROUND MATERIAL/PRELIMINARY STUDIES AND SIGNIFICANCE

- *Describe and provide the results of previous work by yourself or others, including animal studies, laboratory studies, pilot studies, pre-clinical and/or clinical studies involving the compound or device to be studied.*
- *Include information as to why you are conducting the study and how the study differs from what has been previously researched, including what the knowledge gaps are.*
- *Describe the importance of the knowledge expected to result*

- Studies evaluating the accuracy of HbA1c and fructosamine values in patients with T2DM and CKD 3b-5 is scarce. A pilot study by Konya, Nq, Cox, et al., evaluated the accuracy of HbA1c in 15 T2DM patients with CKD3-4 receiving iron or erythropoiesis and concluded that other glycemic markers such as fructosamine or glycated albumin maybe valuable markers in assessing glycemic control in this patient population. Another pilot study by Vos, Schollum, et al., evaluated HbA1c, glycated albumin, and fructosamine in 25 patients with CKD 4-5 matched with T2DM patients with no renal dysfunction. These patients wore a CGM device for only 48 hours. The results of this study indicated that glycated albumin was a better marker than fructosamine and HbA1c in patients with CKD 4-5.
- This investigation is an attempt to add to the current available literature by assessing the accuracy of HbA1c and evaluating if fructosamine and/or CGM data are better tools for short term and long-term diabetes management in patients with CKD 3b-5 (not on hemodialysis (HD)) specifically. Our aim is also to assess the incidence of hypoglycemic and hyperglycemic excursion in these patients by CGM analysis.
- This study allows us to understand which marker (HbA1c, fructosamine, CGM data) is most reliable for diabetes management in patients with CKD 3b-5. Hypoglycemia in this specific subset of patients poses significant risks to increase morbidity and mortality. Improvement in such knowledge of glycemic control will lead to decreased morbidity and mortality in this population.

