7. ELIGIBILITY CRITERIA

- *Describe the characteristics of the subject population, including their anticipated number, age, ranges, sex, ethnic background, and health status. Identify the criteria for inclusion or exclusion of any subpopulation.*
- *Explain the rationale for the involvement of special classes of subjects, such as fetuses, pregnant women, children, prisoners or other institutionalized individuals, or others who are likely to be vulnerable. You cannot include these populations in your research, unless you indicate such in the protocol*
- *Similarly, detail exclusionary criteria: age limits, special populations (minors, pregnant women, decisionally impaired), use of concomitant medications, subjects with other diseases, severity of illness, etc.*

- We anticipate recruiting 80 subjects for this study. We anticipate a fair distribution of males and females, Caucasians, African Americans, and people from other ethnic groups. We anticipate that most patients in this age group are relatively healthy with possibly 1-5 past medical health problems.
- Inclusion Criteria: patients who are 18 years and older with the ability to speak and understand English and with T2DM AND CKD stages 3b-5. Vulnerable populations would include elderly and minorities, as listed in section 26 below for vulnerable populations. There are minimal risks of participating in this study for all subjects including vulnerable populations.
- Exclusion criteria: patients with Type I DM, ESRD on HD, hemoglobinopathies, who have received red blood cell transfusions in the last 12 weeks, with hemoglobin <9, current use of acetaminophen on a daily basis, steroid treatment in the prior 12 weeks, greater than 50% change in diabetes medications or new diabetes medications started in the prior 12 weeks, patients who are currently pregnant.

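### HbA1c and fructosamine share one CGM reference of 7 to 14 days, so this study alone cannot rank HbA1c below fructosamine or attribute HbA1c scatter to CKD

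*Combined protocol and SAP*

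**What the plan says.** - **Timing and reference.** Section 11 has the sensor placed on Day 1 ("placing the Freestyle Libre Pro on research subjects for intended use of 14 days") and both markers drawn once, at its removal: "On Day 14, blood will be drawn for HbA1c and fructosamine". In Section 12, "Arithmetic mean glucose (AMG) will be calculated for each patient from" all of that patient's CGM readings. The minimum is one week: "Patients with less than 7 days of CGM measurements will be excluded from analysis".
- **Same yardstick for both.** Section 12 regresses AMG on HbA1c and then states: "The same analysis will be performed to establish the relationship between AMG and serum fructosamine". Section 10 makes the HbA1c correlation a primary endpoint and the fructosamine correlation a secondary one. Section 12 gives no method for comparing the two.
- **Intended conclusions.** Section 3: "This study allows us to understand which marker (HbA1c, fructosamine, CGM data) is most reliable for diabetes management in patients with CKD 3b-5". Section 4 hypothesizes "significant variability in the serum HbA1c values when compared with calculated HbA1c from CGM readings".
- **Look-back.** Section 7 excludes transfusion and steroid treatment over the preceding 12 weeks, and "greater than 50% change in diabetes medications or new diabetes medications started in the prior 12 weeks". Section 16 withdraws a patient whose diabetes medication is changed during monitoring.

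**The concern.** The eligibility rules treat the previous 12 weeks as relevant to the markers, but the reference covers at most the last two of them. If HbA1c reflects a longer period than fructosamine, a real change in glucose before the sensor was placed appears as disagreement between HbA1c and AMG, while fructosamine is affected less. That disagreement would run in the direction of the study's own hypothesis and could be read as HbA1c inaccuracy caused by CKD. It could also place fructosamine above HbA1c when both track their own averaging period equally well. At stake are the interpretation of the first primary endpoint and the ranking of markers promised in Section 3.

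**Working it through.** **1. What the documents give.** The reference is 14 days of a 12-week (84-day) look-back: 14/84 = 16.7%. At the 7-day minimum it is 7/84 = 8.3%. The target is n = 80, stated without a derivation, so there is no plan figure to reproduce. The documents give no averaging window for either marker, no within-patient drift and no expected correlation.

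**2. Assumptions, none from the documents.** Six 2-week glucose blocks per person; between-person SD 45 mg/dL; within-person drift SD s of 0 to 30 mg/dL with lag-one correlation φ of 0.3 or 0.6. HbA1c averages 12 weeks, with flat or linearly declining weights. Fructosamine averages 4 weeks, with flat weights or 75/25 in favour of the last two weeks. Each marker correlates 0.85 with the mean of its own window, so the two are equally good by construction.

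**3. Formula.** Observed r = 0.85 × Cov(own-window mean, last block) / √[Var(own-window mean) × Var(last block)].

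**4. Worked case, s = 30, φ = 0.3.** Var(last block) = 45² + 30² = 2925.
- HbA1c, flat: Cov = 2025 + (900/6)(1 + 0.3 + 0.09 + 0.027 + 0.0081 + 0.00243) = 2239.1. Var = 2025 + 900 × 9.919/36 = 2273.0. r = 0.85 × 2239.1/√(2273.0 × 2925) = 0.85 × 0.868 = 0.74.
- Fructosamine, 75/25: Cov = 2025 + 900(0.75 + 0.25 × 0.3) = 2767.5. Var = 2025 + 900(0.5625 + 0.0625 + 2 × 0.75 × 0.25 × 0.3) = 2688.75. r = 0.85 × 2767.5/√(2688.75 × 2925) = 0.85 × 0.987 = 0.84.
- Fructosamine, flat: Cov = Var = 2025 + 900 × 0.65 = 2610. r = 0.85 × √(2610/2925) = 0.80.

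**5. Range over both φ and all weightings.**

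| Drift SD (mg/dL) | HbA1c r | Fructosamine r |
|---|---|---|
| 0 | 0.85 | 0.85 |
| 10 | 0.83-0.84 | 0.84-0.85 |
| 20 | 0.79-0.82 | 0.83-0.85 |
| 30 | 0.74-0.79 | 0.80-0.84 |

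**6. What a comparison at n = 80 would show.** Studies were simulated under the same model, with a two-sided 5% test for dependent correlations (2.5% expected in each direction). At drift SD 30, fructosamine comes out nominally significantly better in roughly 8% to 55% of studies. The top of that range needs flat 12-week HbA1c weights together with recency-weighted fructosamine. Declining HbA1c weights bring it to about 19-29%, and flat 4-week fructosamine weights as well to about 8-11%. Without drift, neither marker is favoured.

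**7. Scatter, under a second set of assumptions.** Take daily glucose with a drift half-life of 14 days, and linearly declining weights over 84 days for HbA1c and 21 days for fructosamine. For drift SD 10 to 30, window mismatch alone contributes an SD of 5.8 to 17.3 mg/dL for HbA1c and 0.7 to 2.2 mg/dL for fructosamine.

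**8. Precision for scale.** At r = 0.80 and n = 80, atanh(0.80) ± 1.96/√77 = 1.099 ± 0.223, which gives a 95% CI of 0.70 to 0.87.

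**The case against.** The strongest reply is that the 12-week rules are themselves the plan's protection. Excluding transfusion, steroids, new diabetes drugs and larger drug changes, and withdrawing patients whose drugs change during monitoring, selects people whose last 14 days should resemble the weeks before. That stands, and it reduces the mismatch. It does not remove it, because drug changes of 50% or less and drift from diet, illness or declining renal function remain possible.

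Second, the bias is nil with stable glucose and about 0.01 in r at drift SD 10, well inside the sampling error of a single correlation at n = 80. This also stands. However, bias does not shrink with sample size, and at larger drift it is no longer trivial.

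Third, the averaging windows are outside assumptions, and the plan contains no formal test of one marker against the other; the ranking appears only in the statement of significance in Section 3. That is correct. It also means that Section 3 promises a ranking for which Section 12 offers no method, so readers would compare two correlations by eye.

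A reader might infer that the design necessarily favours fructosamine and inflates HbA1c discordance. The documents do not support that: they contain nothing on drift or averaging windows, and the effect disappears if glucose is stable.

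**Conclusion.** The concern holds as a limit on interpretation. Both markers are judged against one CGM mean of 7 to 14 days, the eligibility and withdrawal rules only partly protect against earlier glucose change, and the plan neither states the limit nor examines it. If HbA1c averages over a longer period than fructosamine, drift can lower the HbA1c correlation more and add scatter not due to CKD.

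The size is unknown. Under the assumptions above it runs from nothing (no drift), through about 0.01 in r (drift SD 10), to HbA1c at 0.74-0.79 against fructosamine at 0.80-0.84 (drift SD 30). No single false-positive rate within the 8% to 55% range should be quoted as the expected one, since it depends on the assumed weights. The planned correlations remain valid as measures of agreement with concurrent glucose. What they do not support alone is a ranking for long-term control or attribution of the scatter to CKD.

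**What to change.** 1. In Sections 3 and 12, limit the marker comparison to agreement with concurrent 14-day glucose. State that neither a ranking of HbA1c below fructosamine for long-term control nor attribution of HbA1c scatter to CKD follows from it alone.
2. Pre-specify a sensitivity analysis of the HbA1c-AMG and fructosamine-AMG correlations and regressions in patients with no diabetes-drug change in the prior 12 weeks. Record as a study variable the drug history already needed to apply the Section 7 criterion. Do not define stability by agreement between a chart HbA1c and the Day 14 value: that selects patients on the marker under test and can bias the result in favour of HbA1c.
3. Report the difference between the two dependent correlations with a 95% CI, overall and in that subset, in place of an informal comparison. The wording in item 1 governs how it is interpreted.

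The cost is revised wording, one recorded variable and one extra analysis, with no added sensors, visits or blood. The downsides are a smaller sample in the sensitivity analysis and a narrower claim. The subset addresses drug-related change only; non-drug drift remains a stated limitation.
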